7. STUDY DURATION/STUDY TIMELINE

Stage 1: recruitment and study procedures, fall 2013-Fall 2014

Stage 2: data analysis, fall 2014- winter 2014

Stage 3: publication, 2015

8. STATISTICAL CONSIDERATIONS

Measures

1. Detection rate of upper intestinal lesions in known IBD – CD undergoing WCE vs radiologic modality.
2. Definitive diagnosis of SB involvement of patients undergoing WCE vs radiologic modality in indeterminate IBD.
3. Complication rate for WCE vs 1st radiologic testing
4. Retention rate of WCE
5. The Crohn's disease activity index and its relation with the findings on both modalities
6. Lewis score on WCE

Sample size determination

With a sample size of 34 participants we will have 80% power probability to detect the 23 % difference in IBD small intestinal MRE findings and WCE detection rate similar to previously reported pediatric studies [11]. This determination uses a Chi-Square test and a two-sided significance level of 0.05. Subjects whose MRE results show findings that are contraindicated with WCE will be considered screen failures. We anticipate around 20% screen failure rate and intend to recruit 40 subjects to obtain a sample size of 34 evaluable subjects.

Data Analyses

The disease activity detection rate of MRE and WCE will be compared using McNemar's test and Chi square test. The sensitivity and specificity of both tests will be calculated based on a gold standard of classifying disease activity using Crohn's disease activity index (CDAI). The person correlation coefficient or spearman rank correlation coefficient

will be utilized to assess agreement between lewis capsule endoscopy score and CDAI. All p values will be 2 sided with statistical significance evaluated at 0.5 alpha level.

HUMAN SUBJECTS

Institutional Review Board (IRB) Review and Informed Consent

This protocol, and any subsequent modifications, will be reviewed and approved by the Pediatric IRB at The Children's Mercy Hospital & Clinics.

We request a partial Waiver of HIPAA Authorization for pre-recruitment activities.

Potential participants will be identified at the time of a clinic appointment or prior to their scheduled MRE appointment in radiology. IBD program coordinators or GI providers will notify a research staff member of a potential participant's eligibility. The family will be approached at a clinic visit about participation. If the research staff is notified at a time that the family is not in the clinic a member of the study team will call the family to introduce the study to them briefly and ask if they can talk with them about the study prior to their MRE. A recruitment flyer and permission assent form can be sent to the family prior to the appointment via e-mail, fax or postal mail should they request it. The recruitment flyer will also be made available in the GI Clinic.

Prior to drawing any blood or performing any other procedures related to this study, the permission/assent form or consent form will be reviewed carefully with the participant (and parent) in person or by telephone in extenuating circumstances (i.e. out-of-state non-custodial parent, divorce, or separation).

Telephone consenting may be necessary for this study due to fasting procedures required prior to the subjects standard of care visit so the subject may continue at the same visit with research procedures. All questions will be answered and signatures will be obtained by study staff from the parent before procedures begin on the child. The PI will ensure the procedures for securing telephone consent are followed.

Subject Confidentiality

Paper/physical Documents: These documents will be stored in a file cabinet in the locked research room in the GI clinic:

- Signed Permission/Assent/Consent – will contain subject and caregiver name and subject MRN, date of consent, retained indefinitely.
- Paper Data Collection Forms – subject study ID, date of service, retained indefinitely

Electronic Documents: These documents will be kept on the secure internal CMH server, in a restricted access folder):

- Data Collection Forms – subject study ID, date of service, retained indefinitely

- Master Participant List - subject name, MRN, date of service, assigned study ID number, retained indefinitely.
- Pre-recruitment Log – subject name, MRN, date of MRE, deleted upon completion of enrollment.
- Data Collection Database - de-identified, retained indefinitely

WCE software - The images from the study and subject name, MRN, date of service, capsule ID number and date of birth will be retained indefinitely on the hard drive. The information entered into the medical record will be retained indefinitely.

Study Modification/Discontinuation

The study may be modified or discontinued at any time by the IRB, the OHRP, the FDA or other Government agencies as part of their duties to ensure that research subjects are protected.

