2. BACKGROUND

Crohn's Disease CD represents a chronic idiopathic disorder primarily involving the gastrointestinal tract. Although any part of the gastrointestinal tract can be involved, the most common pattern in paediatric patients is ileocecal involvement. More proximal small intestinal involvement is more common in pediatric patients with a prevalence of up to 20%[1]. The clinical presentation and sequelae of small intestinal involvement in Crohn's Disease is varied and include nutritional sequelae resulting in growth delay and including iron deficiency anemia, stricture formation, obscure abdominal pain and eventually obstruction[1,2]. Small intestinal screening in suspected Crohn's Disease and periodic small intestinal surveillance in known cases is the current accepted standard of care [1]. There are several modalities that can be employed toward visualizing the small intestine although there is no gold standard[1]. Options include contrast studies including small bowel series and computed tomography enterography (CTE). Gadolinium enhanced MRI imaging (GAD MRI) of the abdomen and small bowel enema are technically more demanding but may be more sensitive in early disease.

There is growing concern with recurrent radiation exposure particularly from routine radiologic modalities in children [3], this is especially relevant in pediatric Crohn's Disease in so far as CT enterocolysis abdomen and small bowel series are often seen as complementary [3]. Although small bowel series is accepted as a routine diagnostic modality in pediatric IBD if fluoroscopy time is kept to a minimum, its limitations are well defined and are especially relevant in the early stages of IBD wherein fistulising, stricturing disease is less common. Magnetic resonance enterography (MRE) has a diagnostic effectiveness comparable to other radiological modalities for evaluation of adult patients with CD, [1,2]but without radiation exposure. However it is limited by expense, the availability of the requisite equipment and software, need for sedation in pediatric population, limited expertise in accurate interpretation especially in early lesions such as are more common in pediatric IBD, and overall insensitivity to early mucosal lesions including vascular abnormalities.

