Alternative modalities for small bowel imaging are being studied and include the routine use of wireless-video capsule endoscopy (WCE) which allows visualization of the small-bowel mucosal lesions in Crohn's disease [4]. Because the risk for capsule retention in suspected or established Crohn's disease is significantly increased; in some series up to 13%; pre WCE small bowel imaging or patency capsule has become standard of care.

The main indications for WCE in Crohn's disease are to establish the diagnosis, to assess disease prognosis, disease activity, and mucosal healing post therapy, and to define the extent and severity of disease [5]. A small, prospective study of 27 patients suspected to have Crohn's disease, revealed a sensitivity of 93% and specificity of 84% for the WCE examination compared to surgical and enteroscopic tissue samples, and demonstrated a significant change in their management [6]. Another prospective randomized blinded study adults (N = 21) reported the sensitivity and specificity of CD in terminal ileum were 100% and 91% by WCE[7]. Jensen suggested WCE as first line modality for detection of small bowel CD beyond the reach of colonoscopy [7]. In adults with known CD, Karoui et al evaluated WCE in a prospective study (N = 20) comparing it to radiological techniques and concluded that WCE is more accurate in detection of small bowel lesions in CD[8].

In a small retrospective study (N=7), most older children and adolescents with unexplained growth failure and normal small bowel series were found to have Crohn's disease involving the small intestine [9]. A recent prospective study performed in 60 pediatric patients with suspected Crohn's disease showed both MRE and WCE appeared complementary methods for the detection of Crohn's disease in suspected CD patients. Both have a high degree of accuracy, sensitivity, and specificity at 98.3%, 100%, 97.6%, and 91.9%, 90.9%, 92.3%, respectively [10]. Another large prospective study in children (N=117) with established or suspected CD demonstrate a statically significant diagnostic yield of WCE in reclassifying indeterminate colitis IC into CD (60%), detection of CD lesions in known CD (41%) and establishing new diagnosis in suspected CD(50%) compared to other radiological modalities[11].

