4. TARGET STUDY POPULATION SPECIFICS

Study participants (n=50) ages 4 – 17.99 years of age will be recruited for this study. Patients will be identified for recruitment after an initial evaluation in gastroenterology clinic at Children's Mercy (CM), if they are diagnosed with IBD and planned to have MRE as part of standard of care for clinical indication to evaluate small bowel disease.

Inclusion Criteria:

- Patients aged 4 to 17.99 years at time of investigation
- IBD/CD and IBD/IC diagnosed based on standard clinical – histologic criteria
- Patient is scheduled to have MRE as standard of care for evaluation of disease severity/ complication.
- Signed permission/assent/consent

Exclusion Criteria:

- IBD diagnosis not established
- Recent intestinal tract surgery / resection involving small bowel
- Use of NSAIDs 4 weeks prior to the Capsule endoscopy study.
- Patients are on prokinetic medication.
- Swallowing disorders, esophageal stricture or patients unable to swallow the capsule.
- Presence of gastrointestinal obstruction or ileus.
- Patient with implanted electro-medical device or pacemakers.

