6. DATA COLLECTION

Data Collection Procedures

- The subject's medical record will be reviewed for data collection to include but not limited to, subject demographics, medical and surgical history, imaging results initial disease presentation and patient current clinical status. Data will be collected on a separate paper data collection form.
- The capsule images will be independently interpreted by the PI initially and then confirmed by two gastroenterologists with 4 - 10 years of experience in capsule endoscopy. The results will be reported in the subject's medical record as they would be for standard of care in compliance with the CMH policy on medical record documentation of research subjects. The subjects regular GI provider will review the results of the WCE and consider the results when making decisions about the subjects treatment plan. We will be using the capsule endoscopy data collection form including the Lewis scoring system that is automatically

calculated and included in the RAPID® software. Lewis score is a WCE ranking of inflammatory activity into three levels based on erythema, stenosis, edema and erosions in small intestinal tertiles: 1) no disease or clinically insignificant disease ($LS < 135$); 2) mild disease ($135 \leq LS \leq 790$); and 3) moderate or severe disease ($LS > 790$).

- The study will be considered negative if no abnormalities were seen and as positive if clear abnormalities of the SB mucosa (i.e. ulcerations, erosions, polyps, vascular lesions, and bleeding lesions) were observed. White lesions within a crater with surrounding erythema were considered ulcers, whereas small superficial white lesions, even with surrounding erythema, were considered erosions. If no abnormalities or non-specific findings (such as erythematous spots or mucosal breaks) were seen the examination was considered non-specific or normal.
- The examiners of WCE and MRE will be blinded to each other's findings but will be aware of the patient's history and laboratory data.
- To reduce variation in MRE readings, one radiologist will retrospectively review the MRE for all subjects to provide a consistent assessment of the extent of the subjects' disease.

Records to be kept

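### Measure 2 calls an unverified small-bowel finding a definitive diagnosis, and the only positivity rule lets non-inflammatory lesions count towards it

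*Combined protocol and SAP*

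**What the plan says.** Section 8 (Statistical Considerations, Measures) gives the second measure as "Definitive diagnosis of SB involvement of patients undergoing WCE vs radiologic modality in indeterminate IBD". The word *definitive* is not defined there or elsewhere, and the Data Analyses paragraph contains no analysis specific to this measure.

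The only rule for calling an examination positive is in Section 6 (Data Collection). It is worded for small-bowel mucosa, so I read it as the WCE rule. The examination is classed "as positive if clear abnormalities of the SB mucosa (i.e. ulcerations, erosions, polyps, vascular lesions, and bleeding lesions) were observed". The same bullet adds: "If no abnormalities or non-specific findings (such as erythematous spots or mucosal breaks) were seen the examination was considered non-specific or normal". No positivity rule is given for MRE.

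On verification, Section 2 (Background) says: "There are several modalities that can be employed toward visualizing the small intestine although there is no gold standard". The one reference standard named in Section 8 is the CDAI, used to classify disease activity.

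On reading, Section 6 says of WCE: "The capsule images will be independently interpreted by the PI initially and then confirmed by two gastroenterologists". Of MRE it says that "one radiologist will retrospectively review the MRE for all subjects to provide a consistent assessment".

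**The concern.** The label and the data do not match. A definitive diagnosis of involvement needs something beyond the two index tests to settle whether the small bowel is involved. The plan schedules no histology, enteroscopy, surgical finding, follow-up or consensus diagnosis for that purpose. The CDAI cannot fill the gap, because active disease and small-bowel involvement are different questions. What the data can show is that a lesion was or was not seen.

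The positivity rule widens the gap. Polyps, vascular lesions and bleeding lesions are not among the features that Section 6 lists as contributing to the Lewis inflammatory score (erythema, stenosis, edema and erosions), yet each one alone makes the examination positive. If Measure 2 is tabulated with the only rule available, such a child is counted as having definitive small-bowel involvement on WCE.

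At stake is the interpretation of the result in indeterminate disease. The Background cites an earlier paediatric study in which WCE reclassified 60% of indeterminate colitis as Crohn's disease. A measure labelled definitive invites a similar statement from this study without the evidence to carry it.

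**Working it through.** The plan states no figure for Measure 2, so there is nothing to reproduce. The check has two parts.

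**1. Can anything in the plan verify the outcome?**

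- Section 2: no gold standard for visualising the small intestine.
- Section 8, Data Analyses: CDAI is the reference for sensitivity and specificity, and it classifies activity only.
- Section 6: two gastroenterologists confirm the WCE reading. This is agreement on the same images, not an independent standard.
- Section 6: one radiologist re-reads the MRE, and no confirming reader is stated.

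No item supplies independent verification of small-bowel involvement.

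**2. How much could an unverified count mislead?**

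Inputs, all from the Background:

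- A study of 60 children with suspected Crohn's disease, figures read in the order MRE then WCE: MRE sensitivity 100%, specificity 97.6%; WCE sensitivity 90.9%, specificity 92.3%.
- A separate study of 27 patients with suspected Crohn's disease, which "revealed a sensitivity of 93% and specificity of 84% for the WCE examination" against tissue samples.
- Prevalence *p* of small-bowel disease in the indeterminate subgroup: not stated. Assumed range 20–60%.

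Formulas:

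- Expected positive fraction = *p* × sens + (1 − *p*) × (1 − spec)
- False share of positives = (1 − *p*) × (1 − spec) ÷ positive fraction

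With no disease present (*p* = 0), the positive fraction is 1 − spec: MRE 2.4%, WCE 7.7% (same source) or 16% (other source).

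| *p* | MRE positive | MRE false share | WCE 90.9/92.3 positive | false share | WCE 93/84 positive | false share |
|---|---|---|---|---|---|---|
| 20% | 21.9% | 8.8% | 24.3% | 25.3% | 31.4% | 40.8% |
| 40% | 41.4% | 3.5% | 41.0% | 11.3% | 46.8% | 20.5% |
| 60% | 61.0% | 1.6% | 57.6% | 5.3% | 62.2% | 10.3% |

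Example, WCE 93/84 at *p* = 20%: false positives 0.80 × 0.16 = 0.128; true positives 0.20 × 0.93 = 0.186; false share 0.128 ÷ 0.314 = 40.8%.

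The false share of WCE positives therefore runs from about 5% (90.9/92.3 at 60%) to about 41% (93/84 at 20%).

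**Which test does a raw count favour?** Set the two positive fractions equal and solve for *p*:

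- Same-source figures: 0.091*p* = 0.053(1 − *p*), so *p* = 0.053 ÷ 0.144 = 36.8%.
- WCE 93/84 against the same MRE figures: 0.07*p* = 0.136(1 − *p*), so *p* = 0.136 ÷ 0.206 = 66.0%.

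Below the crossover, the raw count favours WCE. Above it, the higher sensitivity of MRE outweighs WCE's extra false positives and the count favours MRE.

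**The case against.** The strongest reply is that the plan protects WCE readings better than the label suggests. Three readers are involved, non-specific findings are not counted as positive, and Section 4 excludes "Use of NSAIDs 4 weeks prior to the Capsule endoscopy study". The borrowed specificities come from suspected-disease cohorts, whereas this study enrols children with established IBD, and the documents do not say what those studies counted as positive. Measure 2 is also one of six listed measures, in a subgroup of unstated size, with no test or power attached. All of this stands. It makes the 5–41% illustrative and keeps the point modest. It does not supply a reference standard, and it does not remove polyps, vascular or bleeding lesions from the positivity rule.

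A reader might infer three stronger things that the documents do not support:

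- **That the outcome rests on a single unconfirmed reading.** For WCE this is wrong: two gastroenterologists confirm the first reading. Only independent verification is missing.
- **That the measure is scored in a way that rewards the less specific test.** No scoring rule specific to Measure 2 is stated, so counting positives is an inference. On the only same-source figures, the count favours MRE over more than half of the 20–60% range. The 66% crossover sets WCE and MRE figures from different studies against each other.
- **That neither test could ever give a definitive diagnosis.** The Background says only that no gold standard exists, and it also cites reclassification by WCE. The supportable statement is that this plan cannot verify one. Measure 2 itself concerns small-bowel involvement, not the final choice between Crohn's disease and indeterminate colitis.

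**Conclusion.** The point holds as a matter of definition and labelling. Measure 2 promises a definitive diagnosis that no independent standard in the plan can verify, and under the only stated rule a child with only a non-inflammatory lesion would count as involved on WCE. Any tilt towards WCE is conditional on a prevalence that the documents do not give. The numerical sizes rest on three assumptions: that raw positives are counted, that the cited accuracy figures carry over to this population and rule, and that prevalence lies between 20% and 60%. The mismatch between label and data rests on none of these. It is a cheap improvement to a secondary measure, not a threat to the primary comparison.

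**What to change.** Reword Measure 2 as the proportion of patients with indeterminate IBD who have small-bowel inflammatory lesions suggestive of Crohn's disease on WCE versus MRE. For this measure:

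- count only ulcerations or erosions on WCE, which Section 6 already defines;
- prespecify a matching inflammatory-finding rule for MRE and apply it at the planned single-radiologist re-read;
- tabulate polyps, vascular lesions and bleeding lesions separately;
- report the paired detection proportions with exact intervals;
- make no definitive or reclassification statement unless it rests on evidence other than the study WCE or MRE reading.

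A changed diagnosis in the chart is not enough by itself for the last item. Section 6 places WCE results in the medical record and has the regular GI provider consider them in treatment decisions, so the chart may only repeat the study reading.

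The cost is one reworded line in Section 8, two short reading rules and one extra tabulation, with no new procedures. The small downside is that the WCE figure may be lower and the claim more modest.

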3. STUDY DESIGN

- Prospective single blinded comparison of a cohort of pediatric patients with indeterminate colitis (IC) or Crohn's disease (CD) who are scheduled to undergo

routine small bowel screening or surveillance using MRE. Subjects will swallow a patency capsule (PC) to study bowel patency. If MRE shows stenosis or stricture subject and caregivers will be given the opportunity to continue with the study or withdraw. Those patients, who pass an intact PC, usually within 40 hours, will ingest the wireless capsule endoscopy (WCE). The WCE will be performed within 1 week of completion of MRE. Both modalities diagnostic yields will be compared to detect Crohn's disease lesions/complications and correlate the findings with Pediatric Crohn's Disease Activity Index (CDAI).

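### The paired primary comparison is sized with a chi-square of unstated form and analysed with two tests; the 80% power for 34 children cannot be verified, and the recruitment targets of 40 and 50 conflict

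*Combined protocol and SAP*

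**What the plan says.** Section 3 (Study Design) describes one cohort in which each child has MRE and, once patency is shown, the capsule: "The WCE will be performed within 1 week of completion of MRE". It adds: "Both modalities diagnostic yields will be compared".

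Section 8, Sample size determination, states: "With a sample size of 34 participants we will have 80% power probability to detect the 23 % difference", citing reference 11 for the difference. On method it says only: "This determination uses a Chi-Square test and a two-sided significance level of 0.05". It does not give the two detection rates behind the 23 points, the form of the chi-square, or any assumption about discordant results.

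Section 8, Data Analyses, says the two detection rates "will be compared using McNemar's test and Chi square test". Neither test is named as primary, and the McNemar version is not given.

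On enrolment, Section 8 says: "We anticipate around 20% screen failure rate and intend to recruit 40 subjects to obtain a sample size of 34 evaluable subjects". Section 4 puts the number to be recruited at 50 ("Study participants (n=50").

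**The concern.** A before-and-after or two-test comparison in the same children is carried entirely by the discordant pairs. A sample size that names neither the discordance nor the component rates cannot be checked, and a chi-square for independent groups is not the calculation for this design. A reader cannot tell what the 80% assumes.

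Listing two tests for one primary comparison leaves the choice open until the data are seen. With few discordant pairs, even the McNemar version can decide the result.

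The enrolment text gives two targets, and the smaller one does not yield 34 at the stated loss rate.

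**Working it through.** **Inputs.** From Section 8: 34 evaluable children, 80% power, 23-point difference, two-sided 0.05, about 20% screen failure, 40 recruits. From Section 4: 50 recruits. From Section 2 (Background): 41%, the only rate quoted for lesion detection in known Crohn's disease, from reference 11. The comparator rates of 18% (41 − 23) and 64% (41 + 23) are my assumptions. In the formulas d = 0.23 and d√34 = 0.23 × 5.831 = 1.341.

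**1. Trying to reproduce 80% with a chi-square.**

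*Two-sample, 34 per modality.* Power = Φ{[d√n − 1.96√(2p̄(1−p̄))] / √(p₁q₁ + p₂q₂)}.
- 18% v 41%: (1.341 − 1.96 × 0.645) / 0.624 = 0.123, so power is 55% (57% by full enumeration). About 61 per modality are needed for 80%.
- 41% v 64%: 47% (46% by enumeration). About 73 per modality are needed.
- About 81% appears only at extremes such as 2% v 25% or 75% v 98%.

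*One-sample, n = 34, against a fixed rate p₀.* Power = Φ{[d√n − 1.96√(p₀q₀)] / √(p₁q₁)}.
- Fixed 18%, true 41%: 88%.
- Fixed 41%, true 64%: (1.341 − 1.96 × 0.492) / 0.480 = 0.786, so 78%.
- Fixed 50%, true 73%: 79%.

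The one-sample form comes close to 80% for fixed rates from 30% to 55% and may be where 34 came from. It treats the MRE rate as known, although that rate is measured in the same 34 children.

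**2. McNemar, the test that fits the design.** Let m be the proportion of children with an MRE-only finding. WCE-only is then 0.23 + m, and total discordance is 0.23 + 2m. Power is found by enumerating the number of discordant pairs, Bin(n, 0.23 + 2m), and the WCE-only share of them, (0.23 + m)/(0.23 + 2m).

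Hand check at m = 0: every discordant pair is WCE-only. The exact test needs 6–0 (p = 2 × 0.5⁶ = 0.031; 5–0 gives 0.0625), so power is P[Bin(34, 0.23) ≥ 6] = 83%. The uncorrected test needs only 4–0, giving P[≥ 4] = 97%.

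| Pairs | Version | m = 0 | 2% | 5% | 10% |
|---|---|---|---|---|---|
| 32 | exact | 78 | 67 | 54 | 42 |
| 32 | mid-p | 89 | 78 | 65 | 52 |
| 32 | uncorrected | 96 | 80 | 65 | 52 |
| 34 | exact | 83 | 71 | 58 | 45 |
| 34 | mid-p | 92 | 81 | 68 | 55 |
| 34 | uncorrected | 97 | 82 | 68 | 55 |
| 40 | exact | 92 | 81 | 68 | 54 |
| 40 | mid-p | 97 | 88 | 76 | 62 |
| 40 | uncorrected | 99 | 88 | 76 | 63 |

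(Power, %.) With 34 pairs, 80% holds only while m is at most about 0.4% (exact), 2.1% (mid-p) or 2.4% (uncorrected). One child in 34 is 2.9%, and at that rate power is 66%, 76% and 77% respectively. The 10% column is roughly what independent results would give at 18% and 41%: 0.18 × 0.59 = 10.6% MRE-only.

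**3. Does the version matter?** A 4–0 split gives p = 0.046 uncorrected, 0.0625 mid-p and 0.125 exact. A 9–2 split (7/34 = 20.6 points) gives 0.035, 0.039 and 0.065.

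**4. Enrolment.** 40 × 0.80 = 32. 34 / 0.80 = 42.5, so 43. 34/40 implies 15% loss. 50 × 0.80 = 40. 1 − 34/50 = 32% loss.

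**The case against.** The strongest reply is that the 80% may well be right. If MRE finds nothing that WCE misses, all three McNemar versions exceed 80% at 34 pairs. Section 2 supports that direction by describing MRE as insensitive to early mucosal lesions. Section 8 also counts children whose MRE findings contraindicate WCE as screen failures, which may remove some MRE-positive children from the pairs. The 5% and 10% columns are illustrations, with no evidence that they are likely. All of this stands, and it is why the figure is called unverifiable and not wrong. It does not make a near-zero MRE-only rate safe to leave unstated. The Rationale leaves open that the tests are complementary. Section 2 reports 22% incomplete capsule studies in one paediatric series. Section 3 lets families continue after MRE shows stenosis.

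Second, with 50 recruits and 20% loss there would be 40 pairs, and at a 2.9% MRE-only rate power would be 76–84%. That is correct. But 34 is the protocol's own evaluable target, and the 20% covers only MRE contraindications, not failed patency-capsule passage.

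Third, the 4–0 split is about 12 points, half the design effect. At the design effect itself (8–0, 9–1 or 10–2) all versions reject. The choice of version therefore matters mainly below the design effect, as in the 9–2 example.

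Fourth, the component rates may be in reference 11. The protocol should still state them. Finally, 15% loss is arguably close to 20%, so the gap between 32 and 34 is small. The conflict between 40 and 50 is not.

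**Conclusion.** The concern holds. The protocol's wording alone shows four defects: a paired comparison sized with a chi-square of unstated form; no detection rates or discordance; two tests with no primary, one of which ignores the pairing; and two recruitment targets.

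The 80% is not disproved. Under the two tests that the analysis section names, it is reached only near the edge of the range: very low or very high detection rates for a two-sample chi-square, or an MRE-only rate below one child in 34 for McNemar. At one child in 34, power is 66–77%. These figures rest on the stated 23 points, 34 pairs and two-sided 0.05. The MRE-only rates and the 18% and 64% comparator rates are assumptions, shown as a range. This must be fixed because it concerns the primary comparison.

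**What to change.** - In Section 8, Data Analyses, name one McNemar version (exact, mid-p or uncorrected) in advance as the sole primary test. Report the paired difference with its 95% CI, and delete the chi-square for this comparison.
- In Sample size determination, replace the power sentence with one for the version chosen. For the exact test: with 34 pairs and a 23-point difference, power is about 83 / 71 / 58 / 45% if MRE-only findings are 0 / 2 / 5 / 10%. For mid-p use 92 / 81 / 68 / 55%; for uncorrected use 97 / 82 / 68 / 55%.
- State the two assumed detection rates and how the 23 points were obtained from reference 11.
- Use one enrolment figure in Sections 4 and 8, for example the 50 already stated, with the total loss it allows: 50 to 34 is 32%. If 20% total loss is kept instead, 50 gives 40 pairs, and the 40-pair figures should be quoted.

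The cost is text only. The stated power becomes less favourable in most scenarios, and no children are needed beyond the 50 in Section 4.
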